Study recruitment occurs primarily in the hospital after the potentially eligible patients (those currently enrolled in the separate protocol AAAR7350 and interested in learning more about other research studies) have been admitted to the hospital and transferred to an inpatient bed. For some patients, study recruitment may occur post-discharge, up to 6 weeks following participants' presentation to the Emergency Department when they enrolled in the PHS study. Research coordinators for the present protocol will approach these patients, introduce the study and begin the informed consent process. Consenting participants are randomized to the intervention or control condition and complete baseline measures for the present protocol at the pre-training session (i.e., Time 1). Participants are given an electronic tablet device and a brief training on its use at the end of or within several days of this baseline session. For the subset of patients who provide signed consent and the brief tablet training for this intervention study in the hospital but who are then discharged prior to this session, the Time-1 session is conducted by phone while the patients are at home. An additional subset of patients who consent to participate in this study will come to CUMC after hospital discharge to conduct the questionnaires and the brief tablet training of the pre-training session (i.e., Time 1) in person. All participants then complete 8 sessions of the training (intervention or control version) at home twice per week for 4 weeks using the tablet. During this time their adherence to a heart medication is monitored using eCAP devices that they receive during enrollment or in the mail. For participants currently prescribed aspirin but no other heart medication, their adherence to aspirin will be monitored using the eCAP devices. For participants *not* currently prescribed aspirin but who *are* currently prescribed a heart medication other than aspirin, such as a non-aspirin antiplatelet, a beta-blocker, a statin, or an antihypertensive medication, their adherence to this other heart medication is monitored using the eCAP devices. Within several days following the completion of the 4-week training, participants are then contacted by phone for the post-training session (i.e., Time 2), during which they complete the same measures as completed at the Time-1 session. Then, participants return the tablet devices to CUMC researchers using pre-addressed envelopes/packages mailed to their homes. Finally, at 8 weeks after the Time-1 session, participants return the eCAP medication adherence monitoring devices to CUMC researchers also using pre-addressed envelopes/packages boxes.

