If PTSD, FoR, or both are also associated with diminished future time perspective, patients may value future life goals (e.g., maintain long-term heart health by taking aspirin daily) less than more immediate goals (e.g., avoid distressing reminders of past trauma and future mortality), with predictable consequences for health behaviors. Behavioral economics research suggests that diminished future perspective is associated with lower medication adherence among patients with hypertension and diabetes.¹⁷ We will explore the associations among PTSD, FoR, and a measure from the SOBC measures repository that assesses time perspective; the 10-item self-reported Future Time Perspective Scale assesses the extent to which participants conceive of the future as relatively limited or open-ended.¹⁴

Medication adherence. We measure adherence to aspirin objectively using eCAPS (Information Mediary Corp., Ottawa, Canada). Medication bottles with these special caps automatically record the date and time of bottle openings. Medication adherence across a unit of time (e.g., 1 week, 1 month) is computed as the proportion of days that participants took the correct number of aspirin pills. If patients are taking aspirin and other heart medications (i.e., non-aspirin antiplatelets, beta-blockers, statins, or antihypertensives), then the aspirin will be the heart medication they will place in the eCAP bottle to be monitored. However, if patients are taking other heart medications (i.e., non-aspirin antiplatelets, beta-blockers, statins, or antihypertensives) but *not* aspirin, then they will choose which one medication (either a non-aspirin antiplatelet, beta-blocker, statin, or antihypertensive) to put in the eCAP bottle to be monitored.

Threat Perceptions. In a separate protocol we measure perceptions of threat, which are very early indicators of PTSD symptoms at the emergency department.¹¹ This measure is used as part of the eligibility criteria (see above).

Context sensitivity. We measure participants’ ability to identify information about stressful situations that is helpful for the successful and flexible regulation of distress. The Context Sensitivity Index (CSI) presents hypothetical scenarios and asks participants to answer questions about them (e.g., “How much control do you have over what happens next?”).¹²

3. Statistical Procedures

Analysis Plan

Specific Aim 1.

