To measure FoR in ACS patients, and test its associations with ACS-induced PTSD, diminished future time perspective, and nonadherence to medications.

We will test the extent to which the hypothesized measures of the behavior change mechanisms in question (FoR, future time perspective) are intercorrelated in ACS patients with elevated acute stress symptoms. First, to test convergent validity, we will assess zero-order correlations among these measures. Specifically, we predict that—across both groups at Time 1 before the intervention—higher FoR will be associated with lower future time perspective (i.e., lower FTPS). Second, we will test whether higher FoR is associated with higher threat perception symptoms and overall lower proportion of days adherent to aspirin. Third, due to the within-subjects design, we will also assess test-retest reliability from Time 1 to 2, both across and within groups. In this way we will ensure that we have valid and reliable measures of our proposed mechanisms of behavior change.

Specific Aim 2.

To test whether a cognitive-affective intervention reduces FoR in ACS patients.

We will conduct a univariate ANOVA to assess the effect of the four-week intervention on pre-to-post change in FoR, the proposed target mechanism. Prior intervention research in cancer patients showed a small to moderate effect size of a cognitive-affective intervention on FoR symptoms (Hedge's g for difference in health worries from pre- to post-intervention = 0.35). In separate unadjusted tests with pre-to-post change in FoR (and in an exploratory test of future time perspective) as the outcome, we will enter group (intervention, control) as the predictor. We will repeat the tests adjusting for factors that may explain variance in health behavior, including demographic information (age, sex, race, ethnicity), medical severity assessed by GRACE risk score¹⁸ and Charlson comorbidity index,¹⁹ and depressive symptoms assessed by PHQ-8 score.²⁰

Specific Aim 3.

To test whether patients randomized to the intervention are more adherent to aspirin in the 2-month monitoring period within the first several months after their suspected ACS event, and secondarily, whether any intervention effect is explained by reduced FoR.

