We will test this mediational hypothesis using conditional process modeling with the PROCESS macro in SPSS.²¹ Although we will likely have insufficient power to test the question definitively, the results will inform whether a future larger trial is warranted. The behavioral outcome in the model is heart medication adherence from the eCAP data: mean proportion of adherent days in the 2-month monitoring period that occurs within several months after hospital discharge. The predictor is group (intervention, control). The mediator is pre-to-post change in FoR from Time 1 to 2. For a secondary analysis, we will test the outcome as the magnitude of the slope of change in weekly proportion of adherent days during the 2 months. We will evaluate whether there is a significant indirect effect that supports the notion that the intervention vs. the control training engaged the target mechanism in such a way that changes in the target predicted improved heart medication adherence over the month-long intervention.

Exploratory Aim 1.

We will test for off-target intervention effects on future time perspective, as well as the alternative mediation path through improvement in future time perspective.

The test will be structured as for Specific Aim 3 but with pre-to-post change in future time perspective as the tested mediator.

Exploratory Aim 2.

We will test whether the intervention is associated with greater increases in physical activity relative to the control group and whether this association is mediated by changes in FoR or future time perspective.

The test will be structured as for Specific Aim 3 and Exploratory Aim 1 but with physical activity as the tested behavioral outcome measure instead of medication adherence.

Power analysis.

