In prior research with $N = 97$ at Time 1 using a similar intervention in cancer patients, a moderate effect size (Hedges $g = 0.54$) was found for differences in FoR between the intervention ($n = 64$) and control ($n = 36$) groups after 3 months and a somewhat smaller effect size (Hedge's $g = 0.35$) immediately after the 1-month intervention.¹³ Using G*Power 3.1,²² we tested a range of effect sizes for two levels of power. We determined that the present study is conservatively powered to change FoR in a fixed-effects one-way ANOVA with an effect size f of 0.35 or larger with a sample size of $N = 100$ (50 intervention, 50 control), given alpha = .05 and an intention-to-treat design in which missing data due to attrition are handled with multiple imputation.

4. Study Procedures

Patients will be considered for enrollment in the present study who are currently enrolled in AAAR7350 (the PHS study), who signed consent for AAAR7350 within the last 6 weeks (i.e., 42 days), who have indicated they are willing to hear about other research studies, and who have an Elevated Threat Perception score. Consent will be obtained using an IRB-approved consent form.

Pre-training/Time 1: For patients consenting to the study in the hospital, the pre-training session ideally occurs at this same visit. The RA will assess the potential mechanisms of behavior change verbally. At the end of this session, each patient will be given a tablet and an eCAP bottle with a brief explanation of their use. The estimated duration of this session is 45 minutes, including the consent process, questionnaires, and the brief training in the use of the tablet. A subset of patients will complete the consent process and receive the devices (eCAP bottle, tablet) with a brief training in the hospital and will then separately complete the questionnaires verbally by phone within several days. A separate subset of patients will complete the Time-1 session at CUMC sometime after hospital discharge but before 6 weeks (i.e., 42 days) have elapsed from the time of consent to the protocol AAAR7350.

Training phase: Random group assignment to the intervention or control group will be determined in a double-blind way by the programmed tasks on the tablet for each participant.

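### The secondary Aim 3 outcome, the magnitude of the adherence slope, carries no direction as worded; it should be a signed slope, read beside the adherence level

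*Combined protocol and SAP*

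**What the plan says.** Section 3 (Statistical Procedures), Specific Aim 3, sets two adherence outcomes for the same mediation model, with group as predictor and pre-to-post change in fear of recurrence (FoR) as mediator.

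- The main outcome is a level: "mean proportion of adherent days in the 2-month monitoring period that occurs within several months after hospital discharge".
- The secondary outcome is a slope over the 2 months: "For a secondary analysis, we will test the outcome as the magnitude of the slope of change in weekly proportion of adherent days". No sign convention, slope estimator or rule for reading it together with the level is given.

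The intended direction appears on either side of that definition. The aim is "To test whether patients randomized to the intervention are more adherent to aspirin in the 2-month monitoring period", and the model is meant to show that "changes in the target predicted improved heart medication adherence over the month-long intervention".

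The adherence measure is bounded between 0 and 1. Under Measures, Medication adherence, it "is computed as the proportion of days that participants took the correct number of aspirin pills".

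On timing, section 4 (Pre-training/Time 1) says: "At the end of this session, each patient will be given a tablet and an eCAP bottle with a brief explanation of their use". Section 2 (Study Design), having described the 4-week training, adds: "During this time their adherence to a heart medication is monitored using eCAP devices that they receive during enrollment or in the mail". The device is returned 8 weeks after Time 1. Neither section describes an adherence run-in before training.

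**The concern.** A magnitude has no sign. A patient whose adherence falls by 4 points a week and one whose adherence rises by 4 points a week get the same score. If the intervention keeps patients stable while control patients drift downwards, the control arm has the larger magnitude. An analyst following the text would then report more change in control, or a negative intervention effect, when the truth is a benefit. The path from change in FoR to adherence has the same problem, because improvers and decliners are pooled.

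There is a second, separate limit that survives once the sign is restored. Recording begins at about the start of training, so a gain already present in the first week sits in the starting level and not in the slope. Because the proportion is capped at 1, a patient who is fully adherent throughout has slope 0, as does one who never takes the drug.

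The plan says the Aim 3 results will inform whether a larger trial is warranted. A slope result with an undefined direction beside a favourable mean would make that judgement harder, and no rule is stated for resolving it.

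**Working it through.** **Stated figure.** There is none to reproduce. The plan's only power statement concerns FoR, not adherence.

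**Inputs from the documents.** 50 patients per arm, 8 weeks of monitoring, adherence as a proportion of days (7 per week), alpha 0.05. **Assumptions.** Everything about adherence levels, trends and patient variation, and the use of an ordinary least-squares slope per patient.

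**Step 1: loss of direction.** For weeks w = 1 to 8 the slope is Σ(w − 4.5)·y_w / Σ(w − 4.5)², and the denominator is 42. For a straight line this is the total change divided by 7.

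- Adherence 0.60 rising to 0.90: mean 0.75, slope +0.30/7 = +0.043 per week.
- Adherence 0.90 falling to 0.60: mean 0.75, slope −0.30/7 = −0.043 per week.
- Flat at 0.95: mean 0.95, slope 0.

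The first two have the same magnitude, 0.043.

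**Step 2: noise alone makes the magnitude larger at lower adherence.** For a patient with constant daily probability p, the slope has standard deviation √(p(1 − p)/(7 × 42)), and its expected absolute value is √(2/π) = 0.798 times that.

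- p = 0.90: 0.798 × √(0.09/294) = 0.014.
- p = 0.70: 0.798 × √(0.21/294) = 0.021.

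So with no trend in either arm, the less adherent arm still has the larger expected magnitude.

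**Step 3: simulated trials.** 2,000 trials per row, two-sided t-test between arms. In rows 1 to 3 the patient random intercept has SD 1 on the logit scale. In row 4 patient logits have mean 1.4 and SD 1.2 (about 75% adherent). Entries are the percentage of trials with a significant difference.

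| Intervention vs control (assumed) | Mean favours intervention | Signed slope favours intervention | Absolute slope larger in control |
|---|---|---|---|
| 1. Flat 0.95 vs 0.90 falling to 0.60 | 100 | 100 | 100 |
| 2. 0.90 to 0.88 vs 0.88 to 0.70 | 92 | 99.9 | 97 |
| 3. Flat 0.90 vs flat 0.70 | 100 | about 2 (chance) | 53 |
| 4. Flat at about 75% vs falling about 2 points per week | 39 | 99 | 66 |

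Another assumed profile with control declining and intervention stable gave 100% for the signed slope and 90% for the absolute slope. In rows 1 to 4 the absolute slope was never significantly larger in the intervention arm.

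**Step 4: what the signed slope cannot see.** Patient logits as in row 4.

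- Lift from 75% to 85% already present in week 1: the mean detects it in 85% of trials, the signed slope in about 5%, which is chance.
- Intervention higher every week (92% vs 81% on average) with control climbing about 1.5 points per week: the signed slope favours control in 98% of trials, while the mean favours the intervention in about 98%.

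**Step 5: where the signed slope does better than the mean.**

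- Effect building up over the first weeks: signed slope 91% against mean 52% under one assumed profile, and 86% against 58% under another.
- Both arms declining, intervention more slowly: 95% against 29%.

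The simulations test the group effect only. They do not evaluate the indirect effect through FoR.

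**The case against.** The strongest reply is that magnitude here simply means the size of an ordinary slope. The aim asks who is more adherent, the next sentence speaks of improvement, and nothing says absolute values will be taken. That is probably what the sponsor intends. It does not remove the point, because the outcome as written leaves the sign to the analyst.

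A reader might go further and infer that any per-patient slope fails in this design, or that the trial would report failure or harm when patients in fact took more doses. The documents do not support that, for three reasons.

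- The directional mean is the main outcome of the same model. In both unfavourable cases of Step 4 it points the right way, in about 85% and 98% of trials.
- Those cases assume the full benefit is present in week 1, when only about two of the eight sessions have been scheduled. The second also has control adherence climbing throughout. Nothing in the plan predicts either pattern. Where the effect builds up or prevents decline, the signed slope can be the more sensitive measure.
- Replacing the slope with a model of group, week and their interaction would remove the planned test of an indirect effect through change in FoR.

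It is also fair to say that the start of recording is not fixed to the day. The tablet may follow baseline by several days and the eCAP may come by mail, so some patients could have a few days of recording before training and others could start late. That is not a planned baseline period, and the limit on interpretation stands.

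**Conclusion.** The wording should be corrected. Taken literally, the secondary outcome cannot separate improvement from decline, and under assumed profiles in which the intervention prevents a decline it points the wrong way in about 66% to 90% of trials; the more marked profiles in rows 1 and 2 of the table give 97% to 100%. The signed slope favours the intervention in 99% to 100% of trials in all of these. The arithmetic on direction needs no assumptions. The percentages rest on assumed adherence levels, trends and between-patient variation, since the plan gives none.

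The absence of a pre-training adherence period limits how even a signed slope can be read: it is blind to a gain present from week 1 and should not stand without the level. It does not invalidate the slope.

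Severity is minor. This is a secondary analysis, the main adherence outcome has a direction, and the plan already says power for this aim is likely insufficient.

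**What to change.** In section 3, Specific Aim 3:

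1. Delete the words that make the outcome a magnitude. Define it as each participant's signed slope of the weekly proportion of adherent days over the 8 weeks, with a positive value meaning improving adherence, and name the estimator.
2. Keep this signed slope as the secondary outcome in the planned mediation model, so that the indirect effect through change in FoR is still tested.
3. State that the slope is interpreted only beside the main outcome (mean proportion of adherent days) and a display of weekly adherence by arm, because no pre-training adherence is recorded by plan.
4. Optionally, add a logistic mixed model or GEE of daily or weekly adherence with group, week and group-by-week as support for the group effect. It should not replace the mediation test.

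Items 1 to 3 cost a few lines of text, with no new data and no change of software. Item 4 costs one standard analysis of data already collected. The change should be made before adherence is compared between arms, so that the sign convention cannot be chosen from the result.

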We will use the Science of Behavior Change (SOBC) experimental medicine approach to identify, measure, and influence FoR and related cognitive mechanisms (e.g., diminished future time perspective), and determine whether change in FoR is related to change in medication adherence. We will enroll N = 100 patients within 6 weeks of first presenting to the emergency department with suspected acute coronary syndrome who reported elevated early symptoms indicative of risk of developing PTSD (threat perceptions) at the time of their emergency department visit.¹¹ In all participants, we will measure FoR using the Concerns About Recurrence Scale (which we have adapted for ACS).¹³ We will also measure future time perspective using an assay from the SOBC measures repository: the Future Time Perspective Scale,¹⁴ to test their association with FoR and nonadherence. Prior to discharge, we will randomize patients to receive a computerized cognitive-affective FoR intervention [8 sessions (30 min/session; 2/week for 4 weeks)¹³ or control task, to test whether the intervention reduces FoR. The brief intervention has successfully reduced FoR in cancer patients. It trains patients to attend away from threatening disease-related cues (e.g., looking away from the word recurrence and instead toward a neutral word such as categories) and to make benign interpretations of ambiguous, potentially disease-related information (e.g., fatigue reflects lack of sleep, not ACS recurrence). Finally, we will test whether the intervention (and/or improvement in FoR) is associated with greater electronically-measured adherence to aspirin or other heart medications, including non-aspirin antiplatelet, beta-blockers, or statins, in the 2 months after discharge.

Specific Aim 1: To measure FoR in ACS patients, and test its associations with ACS-induced PTSD, diminished future time perspective, nonadherence to medications, and lack of physical activity.

Specific Aim 2: To test whether a cognitive-affective intervention reduces FoR in ACS patients.

Specific Aim 3: To test whether patients randomized to the intervention are more adherent to aspirin in the 2 months after discharge for ACS, and secondarily, whether any intervention effect is explained by reduced FoR.

Exploratory Aim 1: We will test for off-target intervention effects on future time perspective, as well as the alternative mediation path through improvement in future time perspective.

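### Aim 3 asks first whether training improves adherence, but its analysis text names no between-arm estimate and commits only to an indirect effect, which cannot answer that question

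*Combined protocol and SAP*

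**What the plan says.** The combined document states the adherence question twice. Section 1 (Study Purpose and Rationale) says "we will test whether the intervention (and/or improvement in FoR) is associated with greater electronically-measured adherence to aspirin" or other heart medications. In section 3, Specific Aim 3 opens by asking whether "patients randomized to the intervention are more adherent to aspirin in the 2-month monitoring period within the first several months" after the event, "and secondarily, whether any intervention effect is explained by reduced FoR". The randomised comparison therefore leads and mediation follows.

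The analysis paragraph under that aim starts from the mediational hypothesis and the PROCESS macro. It sets the outcome as the "mean proportion of adherent days in the 2-month monitoring period that occurs within several months after hospital discharge", and continues: "The predictor is group (intervention, control). The mediator is pre-to-post change in FoR from Time 1 to 2". A secondary analysis replaces the outcome with the slope of weekly adherence. The paragraph closes with "We will evaluate whether there is a significant indirect effect that supports the notion" that training engaged its target and so improved adherence. That sentence refers to the month of training, although the outcome window is two months. The paragraph also concedes that power is probably inadequate and says the results will feed into the decision about a larger trial.

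Specific Aim 2 is written differently. It names an ANOVA on change in FoR with group as predictor, extends it to future time perspective, and adds "We will repeat the tests adjusting for factors that may explain variance in health behavior". Exploratory Aim 2 (physical activity) takes its structure from Aim 3. The only mention of intention to treat and multiple imputation is in the Power analysis, in the sentence on FoR.

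**The concern.** No total effect, mean difference, confidence interval or group test on adherence is named for the aim's lead question. A team that follows the analysis paragraph literally would report a product of two paths as the Aim 3 result. Randomisation protects the first path (group to FoR) but not the second (FoR to adherence).

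If change in FoR and adherence share a cause, or if taking the medication itself affects fear, the product can be significant when training did nothing for adherence. Section 1 supplies a candidate shared cause: it links PTSD symptoms both to nonadherence and to greater fear of recurrence. That statement concerns the level of fear; a link with change in fear is an assumption.

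The plan does not say what would be concluded if the indirect effect were significant but the arms did not differ in adherence.

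**Working it through.** **Plan's own figures.** None is given for Aim 3. The Power analysis concerns FoR only: f = 0.35 with N = 100 and alpha 0.05. For two equal groups d = 2f = 0.70, which gives 93.4% power. No power value is stated to compare this with.

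**Timing.** Under Study Design, Time 2 falls within days of the end of the 4-week training, and the eCAP is returned 8 weeks after Time 1. So about 4/8, or half, of the outcome is recorded before the mediator is complete.

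**The two results can disagree in either direction.** The total effect is a·b + c′ (a: group to FoR; b: FoR to adherence; c′: direct effect). Assumed standardised paths, N = 100, 2,000 runs each:

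| Paths | Total effect | Indirect significant | Total significant |
|---|---|---|---|
| a = −0.7, b = −0.5, c′ = −0.35 | 0.35 − 0.35 = 0 | 93% | 4.5% |
| a = −0.35, b = 0, c′ = 0.7 | 0.70 | 1.4% | 94% |
| a = −0.7, b = −0.5, c′ = 0 | 0.35 | 94% | 34% |

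**False favourable indirect effects when training does not affect adherence.**

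Inputs:
- From the Power analysis: 50 per arm, and an FoR effect of 0.35 SD (the Hedges g reported immediately after the intervention in the cancer trial).
- Assumed: r, the within-arm correlation of FoR change with weeks 1–4 adherence only (reverse causation) or with each 4-week half (shared cause), and ρ, the correlation between the two halves, 0.5 to 0.7.

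Hand approximation at ρ = 0.6, P ≈ P(a) × P(b):
- P(a): t test, 98 df, noncentrality 0.35 × √(50/2) = 1.75, giving 0.41. At 0.70 SD the noncentrality is 3.5, giving 0.934.
- Partial correlation R of FoR change with the 8-week mean: r / √((1+ρ)/2) for a shared cause, r × √((1+ρ)/2) for reverse causation, with √0.8 = 0.894.
- P(b) = Φ(atanh|R| × √96 − 1.96).
- Example, shared cause, r = −0.2: R = −0.224; atanh|R| × √96 = 2.23; P(b) = Φ(0.27) = 0.606; P ≈ 0.41 × 0.606 = 0.25.

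Simulation: percentile bootstrap, 2,000 runs per cell, 1,000 resamples, ρ = 0.5, 0.6 and 0.7.

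| r | Shared cause: hand / simulated | Reverse causation: hand / simulated |
|---|---|---|
| 0 | 1% / 1% | 1% / 1% |
| −0.1 | 8% / 6–8% | 6% / 4–5% |
| −0.2 | 25% / 22–26% | 17% / 15–18% |
| −0.3 | 38% / 38–40% | 32% / 28–30% |

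- Repeat runs with a Monte Carlo interval gave 13–23% at r = −0.2 and 30–39% at −0.3.
- With 40 per arm (assumed 20% loss, ρ = 0.6) the rates are 10–18% and 22–31%.
- If the FoR effect is 0.70 SD, shared cause at r = −0.2 gives 0.934 × 0.606 = 0.57 by hand and about 55% by simulation.
- With r = +0.2 to +0.3 (ρ = 0.6) the error reverses: the indirect effect is falsely unfavourable in 15–37%.
- The group test is falsely favourable in 2–3% throughout. Among the false favourable trials at r = −0.2 and −0.3, it shows no significant benefit in 95–99%.

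**Precision of the missing estimate.** The 95% CI half-width is t(0.975, 98) × √(2/50) = 1.984 × 0.2 = 0.397 SD. The difference detectable with 80% power is 2.80 × 0.2 = 0.56 SD. With genuine mediation (b path 0.3, FoR effect 0.35 SD) the implied group effect is 0.35 × 0.3 / √((1+ρ)/2) = 0.114 to 0.121 SD. The group test then has 8–9% power, against 38% for the indirect effect.

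**The case against.** A reader might infer that the plan omits the randomised comparison altogether. It does not. The aim statement inside Statistical Procedures commits to it, and the predictor and outcome are fixed, so the estimate comes from the same variables. What is missing is the named contrast, its interval and its rank.

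A reader might also infer that the plan makes a significant indirect effect its test of efficacy or its trigger for a larger trial. The documents do not support that either. The effect is worded as support for mechanism engagement, and the plan says only that the results will inform the later decision, with low power admitted. Even so, the paragraph singles out no other Aim 3 result, and the and/or in section 1 does not settle which result answers the aim.

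The rates depend on an assumed r and FoR effect. At r = 0 there is no inflation, so they illustrate what can happen and do not estimate this trial's error rate.

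The group estimate is also a weak diagnostic. It is non-significant in 95–99% of false favourable trials, but also in 87–89% of trials with a significant and genuine indirect effect. It limits the claim without separating true from false mediation.

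Finally, the intention-to-treat statement can be read as study-wide, and the Aim 2 covariates are described in terms of health behaviour, which hints at wider use. Neither supplies the missing estimate. Future time perspective is not affected, because its group test is named under Aim 2.

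**Conclusion.** The point holds in a limited form. The lead question of Aim 3 has no named between-arm estimate, and the only result the analysis text commits to evaluating cannot answer it. The indirect effect rests on a non-randomised path, the model names no covariates, and about half of the outcome precedes the second FoR measurement. These textual findings need no assumption.

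The size does. With no training effect on adherence and an FoR effect of 0.35 SD, the false favourable rate runs from about 1% at r = 0, through 4–8% at −0.1 and 15–26% at −0.2, to 28–40% at −0.3. It rises further if the FoR effect is larger. The comparison is obtainable and cheap to specify, so this should be corrected in the plan; it does not invalidate the design. Physical activity in Exploratory Aim 2 inherits the same gap.

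**What to change.** 1. Name as the first Aim 3 result the intention-to-treat between-arm difference in mean proportion of adherent days over 8 weeks, with its 95% CI and the multiple imputation already described in the Power analysis. Base any statement that training improved adherence on it, and label the indirect effect secondary and hypothesis-generating.
2. Keep the planned mediation model, and also report it adjusted for the covariates already listed under Aim 2, taken at baseline. These handle measured causes only.
3. Reconcile the closing sentence's reference to the training month with the 2-month outcome window.
4. Report the between-arm difference first for physical activity in Exploratory Aim 2. The Measures text describes no physical-activity instrument, so the outcome needs naming too.

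Optional: a mediation sensitivity analysis with adherence after Time 2 as outcome and weeks 1–4 adherence as covariate. It guards against reverse causation (false favourable about 1%) but not shared causes (10–17% at r = −0.3). It conditions on a post-randomisation variable and cuts power under true mediation from 39–42% to 7–13%. Devices that arrive by mail may also leave the early weeks incomplete.

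The cost is a few sentences and one comparison per outcome; adherence needs no new data. The drawback is imprecision: at about ±0.40 SD, a null between-arm result would not rule mediation out, and the text should say so.
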